#### Assessing for Medication Side Effects

- "Have you had any side effects from your medications " (Y/N)
  - If NO, application skips to the next section
  - $\circ~$  If YES, application prompts promoter to ask the patient: "What problems have you had with your medication "\*
  - Application asks promoter: "Has the patient complained of nausea, vomiting, or persistent diarrhea after taking Metformin " (Y/N)
    - If YES, application prompts promoter to ask patient: "Have you skipped a dose of metformin, or thought about stopping metformin due to these symptoms "
      - If YES, patient is considered to be having significant metformin side effects
      - If NO, patient is not considered to be having significant metformin side effects
    - If NO, application prompts promoter to enter other symptoms in a free text box for review by the physician
  - For patients taking aspirin (for monthly visit only): "In the past month, have you had blood in your stool or stool that is very black and tarry."
    - If YES, patient is advised to stop aspirin and is referred to medical director for further assessment
    - If NO, aspirin is continued

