- At the enrollment visit, CHWs will use the smartphone application to screen patients for appropriate inclusion in the program, establish glycemic targets, assess current glycemic control with hemoglobin A1c and blood glucose, measure height, weight, blood pressure, and waist circumference, assess for the presence of diabetes complications (diabetic ulcers, angina, diabetic eye disease), administer oral medications (metformin and/or glyburide, known locally by its alternate name glibenclamide) based on a medication dosing algorithm, and provide diabetes self-management education.
- CHWs will meet with patients on a monthly basis to assess medication adherence and for adverse effects, glycemic control (with blood glucose), screen for diabetic complications, refill medications with titration as needed (if experiencing medication adverse effects or blood glucose is significantly above or below treatment goals), and provide further diabetes education. Again, these activities will be guided by the smartphone application. Every 3 months, the monthly visit will also include A1c measurement for a more definitive measurement of diabetes control and to allow for titration of medications. Patients who are identified as having complications or who are not meeting treatment goals despite maximal dosing of metformin and glibenclamide allowed by the algorithm will be referred to SLM medical director [name] for definitive meangement.
- After all visits, including enrollment and monthly visits, [name], in addition to the study investigators, will
  review data for all patients seen, including treatment recommendations made by the application and
  carried out by the CHWs, and make any changes to the treatment plan as needed based on his clinical
  judgement.
- Mean hemoglobin A1c and proportion of patients meeting treatment goals (primary endpoints) will be
  assessed at 6 months and compared to baseline, in addition to a number of secondary endpoints and
  safety measures as described in the relevant sections of this protocol. If possible, patients will also be
  followed out to 12 months with reassessment of primary and secondary endpoints.

Version #: 1.0

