## 2.6 Dose Rationale

The standard doses for metformin and glibenclamide used in our program are as follows:

- Metformin: 850 mg, 1500 mg, or 2550 mg per day (850 mg dosed once, twice, or three times daily, respectively)
- Glibenclamide: 2.5 mg, 5 mg, or 10 mg one time daily

In accordance with diabetes treatment guidelines, metformin is the first line medication for all patients in the program and is continued in all patients as long as it is tolerated and there are no contraindications. The standard starting dose of metformin in our protocol is 1700 mg (850 mg twice daily) as 1500 - 2000 mg is thought to be the usual effective dose range.

Also in accordance with ADA and AACE guidelines, patients with initial or repeat A1c ≥9% are placed on dual therapy with metformin and glibenclamide. For patients who are initially started on metformin alone and whose A1c is <9%, glibenclamide is added if they are not meeting glycemic targets despite maximum daily dose of metformin (2550 mg). Though the maximum dose of glibenclamide is 20 mg, most of the hypoglycemic effect of glibenclamide is thought to come at the initial 2.5 mg dose and doses above 10 mg per day are not thought to provide significant additional benefit. For this reason, the maximal dose of glibenclamide used in our program is 10 mg per day.

Glibenclamide does carry a higher risk of hypoglycemia compared to newer sulfonylureas such as glimepiride and glipizide. However, glibenclamide was selected for use in this program because other sulfonylureas are either not readily available in Guatemala or are prohibitively expensive compared to glibenclamide. In addition, though glibenclamide carries a higher hypoglycemia risk than other sulfonylureas, the risk of serious 15

[name]

hypoglycemia (requiring the assistance of another person or hospitalization) is still low, with reported occurrence in only 0.5% of patients in a meta-analysis of sulfonylurea studies.

The application will recommend aspirin for patients with a history of ischemic stroke and CAD to prevent recurrent events and for patients with possible ACS, as long as contraindications are not present. The dose used for ASCVD prevention is 81 mg per day, which is in accordance with current consensus guidelines. The dosage used for treatment of possible ACS is 324 mg, also in accordance with current consensus guidelines.

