### 2.7 Potential Risk and Benefits to Subjects

### 2.7.1 Known Potential Risks

Immediate risks

- The potential immediate risks include the risks of taking metformin, glibenclamide, or aspirin, medications which have been in use for decades and have well-established safety and side-effect profiles.
  - Metformin: The most common side effect of metformin is gastrointestinal distress (e.g. dyspepsia, nausea, vomiting, diarrhea). This usually improves with time and most patients can tolerate these side effects, with only 5% of patients discontinuing the drug completely because of them^36. The most serious reported adverse effect of metformin is lactic acidosis. However, the incidence of this has been found repeatedly to be exceedingly low. In fact, a 2010 Cochrane review found no cases of lactic acidosis over 70,490 patient-years of metformin use, even when patients with some renal impairment were included. Finally, metformin can cause vitamin B12 deficiency with long term use
  - Glibenclamide: The primary potential adverse effect of glibenclamide is hypoglycemia. The proportion of patients taking glibenclamide who will suffer an episode of severe hypoglycemia (requiring the assistance of another for treatment and/or hospitalization) is estimated to be 0.5%
     Aspirin: Significant potential adverse effects of aspirin include gastrointestinal toxicity,
  - hemorrhage, renal toxicity, and hypersensitivity reactions
- Risk of errors in medication administration or recommendations due to user error or application
  malfunction
- Discomfort with finger sticks for blood glucose and hemoglobin A1c measurements

Long-range risks

• Complications of medication adverse effects (e.g. anemia from metformin or aspirin use, renal insufficiency as a related to aspirin use)

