# 6.5 Starting Dose and Dose Escalation Schedule

Metformin will be started at 850 mg once daily and increased to the target dose of 1700 mg after 2 weeks. If not meeting treatment goals after ≥1 month, metformin can be increased to 2550 mg. Patients who are unable to tolerate the 1700 mg dose will take the 850 mg dose.

Version #: 1.0

[name]

Glibenclamide will be used for patients who are unable to tolerate metformin, in addition to metformin if A1c  $\geq$ 9, or if glycemic goals not met despite maximal dose of metformin. Dosing will start at 2.5 mg once per day. If glycemic goals are not met after  $\geq$ 1 month, dose will be escalated to 5 mg once per day and then 10 mg once per day as needed.

Aspirin will be dosed at 81 mg once per day for secondary prevention in eligible patients with history of MI or stroke or patients who have new chest pain and are awaiting medical workup for possible CAD. Patients with high risk chest pain and possible ACS will be treated with aspirin 324 mg (four 81 mg tablets) once while awaiting emergency transport to SLMH.

Please consult Appendix 8, Appendix 10, and Appendix 11 for further information on medication titration protocols

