#### Tx goal< A1c <9

- Not taking medications or nonadherent, no hypoglycemia or hypoglycemia symptoms, no problems with metformin → metformin 1700 mg
- 2. Not taking medications or nonadherent, no hypoglycemia or hypoglycemia symptoms, problems with metformin
  - a. Agrees to take metformin  $\rightarrow$  metformin 850 mg + glibenclamide 2.5 mg
  - b. Refuses to take metformin  $\rightarrow$  glibenclamide 2.5 mg
- 3. Not taking medications or nonadherent, hypoglycemia or hypoglycemia symptoms → metformin 1700 mg
- 4. Not taking medications or nonadherent, hypoglycemia or hypoglycemia symptoms, problems with metformin
  - a. Agrees to take metformin  $\rightarrow$  metformin 850 mg
  - b. Refuses to take metformin, prescribed glibenclamide >2.5 mg  $\rightarrow$  glibenclamide 2.5 mg
  - c. Refuses to take metformin, prescribed glibenclamide 2.5 mg  $\rightarrow$  MD consult
- 5. Taking metformin without problems
  - a. Metformin 500-1000 mg  $\rightarrow$  metformin 1700 mg
  - b. Metformin 1500-2000 mg → metformin 2550 mg
  - c. Metformin 2550 mg  $\rightarrow$  metformin 2550 mg + glibenclamide 2.5 mg
- 6. Taking metformin with problems
  - a. Metformin 500-850 mg, agrees to take metformin → metformin 850 mg + glibenclamide 2.5 mg

[name]

- b. Metformin 500-850 mg, refuses to take metformin  $\rightarrow$  glibenclamide 2.5 mg
- c. Metformin 1000-1700 mg  $\rightarrow$  metformin 850 mg + glibenclamide 2.5 mg
- d. Metformin 2000-2550 mg  $\rightarrow$  metformin 1700 mg + glibenclamide 2.5 mg
- 7. Taking glibenclamide without problems
  - a. Glibenclamide 2.5-10 mg  $\rightarrow$  metformin 1700 mg + glibenclamide current dose
  - b. Glibenclamide 15-20 mg → metformin 1700 mg + glibenclamide 10 mg
- 8. Taking glibenclamide, previous problems with metformin
- a. Agrees to take metformin
  - i. Glibenclamide 2.5-10 mg  $\rightarrow$  metformin 850 mg + glibenclamide current dose
  - ii. Glibenclamide 15-20 mg  $\rightarrow$  metformin 850 mg + glibenclamide 10 mg
  - b. Refuses to take metformin
    - i. Glibenclamide 2.5 mg  $\rightarrow$  glibenclamide 5 mg
    - ii. Glibenclamide 5 mg  $\rightarrow$  glibenclamide 10 mg
- iii. Glibenclamide 10-20 mg  $\rightarrow$  glibenclamide 10 mg
- 9. Taking glibenclamide with hypoglycemia or hypoglycemia symptoms
  - a. Glibenclamide 2.5 mg  $\rightarrow$  metformin 1700 mg
  - b. Glibenclamide 5 mg  $\rightarrow$  metformin 1700 mg + glibenclamide 2.5 mg

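### The follow-up questions on metformin side effects have no recall period, so an old reaction can cut a now-tolerated 1700 mg dose to 850 mg

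*Combined protocol and SAP*

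**What the plan says.** Appendix 3 (Assessing for Medication Side Effects) opens with "Have you had any side effects from your medications". If the patient then describes nausea, vomiting or persistent diarrhea after metformin, the health worker asks "Have you skipped a dose of metformin, or thought about stopping metformin due to these symptoms". On a yes, the "patient is considered to be having significant metformin side effects".

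Section 7.4.2 says that monthly visits mirror enrollment, and none of its listed exceptions rewords these questions. It also makes the month-3 visit the same apart from A1c testing and the A1c-based algorithm. Section 10.3 repeats the open question for each visit, again undated.

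On dose:
- Section 6.5 states: "Patients who are unable to tolerate the 1700 mg dose will take the 850 mg dose".
- The overview in Section 2.1 allows titration at monthly visits "if experiencing medication adverse effects".
- Section 2.6 explains the 1700 mg starting target by noting that "1500 - 2000 mg is thought to be the usual effective dose range".
- Section 2.7.1 says of the gastrointestinal effects: "This usually improves with time and most patients can tolerate these side effects".
- Appendix 8 sends patients who take "Metformin 2000-2550 mg" with problems down to 1700 mg. In the band above goal and below 9%, it also adds glibenclamide 2.5 mg.

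**The concern.** The questions cover any time in the past, but the answer is treated as a statement about now. A patient whose reaction occurred on 2000-2550 mg, and who was cut to 1700 mg for it, can truthfully say yes to both questions at the next visit while having no trouble on 1700 mg. The answer selects the metformin-problem rows of Appendix 10 or 11, and these cut 1700 mg to 850 mg. A tolerated dose inside the plan's usual effective range is then replaced by one below it. When glucose or A1c is above goal, glibenclamide is often added or raised in its place. Section 2.7.1 names glibenclamide as the study drug with probably the greatest potential for harm.

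**Working it through.** The plan gives no figure for this point, so the check is a trace of the written rules.

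**1. Is the missing period just house style?** No. In the same appendix, the aspirin bleeding item (marked for monthly visits only) and the adherence item ask about the past month. The hypoglycemia symptom item (Appendix 4) and the chest-pain and vision items (Appendix 6) are dated too. Section 2.7.2 says that patients are asked about metformin effects monthly. That sets how often the question is put, not the period it covers.

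**2. First cut.** For patients on metformin alone with problems, all five Appendix 8 bands up to A1c 14 send 2000-2550 mg to 1700 mg: row 4d (below 5.7), 4d (5.7 to below 6.5), 5d (6.5 to goal), 6d (above goal to below 9) and 6d (9 to 14). At follow-up, row 3d sends 2550 mg to 1700 mg.

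**3. Second cut.** The state traced is metformin 1700 mg with glibenclamide 0, 2.5, 5 or 10 mg, in an adherent patient with no hypoglycemia symptoms who took any glibenclamide the day before. The rows compared are:
- Appendix 10: rows 1 and 13 (no problems) against 3c and 17c onward (problems).
- Appendix 11: rows 1b and 13 against 3c and 15c onward.

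Each band has four cells, one per glibenclamide dose.

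| Band | Metformin, no problems | Metformin, problems | Glibenclamide higher with problems |
|---|---|---|---|
| App. 10, FBG below 80(90) | 1700 in 4 | 850 in 4 | 0 |
| App. 10, 80(90) to 130(150) | 1700 in 4 | 850 in 4 | 0 |
| App. 10, 130(150) to 180(200) | 1700 in 4 | 850 in 4 | 3 |
| App. 10, 180(200) to 400 | 2550 in 4 | 850 in 4 | 3 |
| App. 11, A1c 5 to 6 | 1700 in 4 | 850 in 4 | 0 |
| App. 11, 6 to goal | 1700 in 4 | 850 in 4 | 0 |
| App. 11, goal to 9, glucose above range | 2550 in 4 | 850 in 4 | 3 |
| App. 11, 9 to 14, glucose above range | 1700 in 1, 2550 in 3 | 850 in 4 | 2 |

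Totals:
- With problems: 850 mg in 32 of 32 cells.
- Without problems: 1700 mg in 4+4+4+4+4+1 = 21 cells and 2550 mg in 4+4+3 = 11.
- Glibenclamide is higher in 3+3+3+2 = 11 of the 16 above-goal cells and in 0 of the other 16. Of the five above-goal cells with no rise, four are already at 10 mg. In the fifth, both rows add 2.5 mg.
- Dose: 850/1500 = 0.57 of the lower end of the plan's effective range.

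**4. One patient.** Enrollment at A1c above goal and below 9, on 2550 mg with problems: row 6d gives 1700 mg plus glibenclamide 2.5 mg. At month 1 the patient tolerates this, and fasting glucose is between 130 and 180 mg/dL. Row 13 would continue both drugs. If the old episode is reported, row 17c gives 850 mg plus glibenclamide 5 mg.

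**The case against.** The surrounding text points toward current symptoms. Monthly visits are there to check tolerance, the scoring phrase is in the present tense, and titration is tied to patients who are having effects. The tables label earlier metformin problems separately in the glibenclamide-alone rows, so a resolved reaction could be said to belong in the no-problem rows. Three answers must also line up: the patient volunteers an old symptom to an open question, the health worker records it as gastrointestinal, and the patient says yes to skipping or thinking of stopping. Appendix 3 explains that the opening was left open to avoid prompting positive answers. Health workers are paired with a coordinator for the first several months and can phone for advice, and the physician reviews each visit within 1 week.

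Much of this stands. It makes the error uncommon on a sensible reading, and it rules out calling the plan clearly wrong. It does not close the gap. The quoted items are the script put to patients, and the application is meant to spare health workers such judgements. Physician review comes after dispensing, and the plan describes no field that dates the symptom. The undated wording also has a real purpose elsewhere: Appendix 3 puts the same questions to patients who have stopped all medication, where past reactions are what is wanted. That is a reason to date the questions selectively.

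**Conclusion.** The point holds as a minor ambiguity in the follow-up script. Read literally, it allows a second metformin cut that Section 6.5 does not intend. It rests on two assumptions: that the question is put as written, and that some patients answer about an episode before their last dose change. The documents do not give the share who would do so (0 to 100% is possible). Given the safeguards and the narrow group, it is probably low.

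Four stronger readings are not supported:
- **32 of 32 as an error rate.** The metformin-problem rows are meant to give less metformin. The count shows the consequence of the classification, not how often it is wrong.
- **An effect on A1c or the primary endpoints.** Nothing in the documents allows one to be estimated.
- **Inflation of the secondary endpoint on metformin adverse effects.** The plan does not say how that prevalence is built from visit answers.
- **Patients cut from 1700 to 850 mg are wrongly held there.** Keeping them at 850 mg agrees with Section 6.5.

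**What to change.** In the monthly and month-3 modules, for patients currently prescribed metformin 1700 or 2550 mg, begin both questions with *Since your last visit*. For a patient cut at the previous visit, that interval is the time on the new dose, so the answer concerns the dose being judged. A reaction that began and ended within the interval would still count.

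Keep the undated wording:
- at enrollment;
- for patients not currently on metformin, because Appendix 3 describes no other question that would identify earlier metformin problems, and losing that information could send glibenclamide-alone patients to 1700 mg;
- for patients on 850 mg, whose handling is not in question.

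No stored intolerance marker or extra symptom item is needed. A marker holding patients at 850 mg would override the existing rows that raise a symptom-free patient from 850 to 1700 mg (rows 1a and 13a in the above-goal bands). It could add glibenclamide instead, which would be a change of treatment policy.

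The cost is one conditional wording change, a matching line in Appendix 3, and re-testing of the affected branches. No visits or tests are added.

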#### Assessing Medication Adherence

• "In the past month, how often did you take your medication as the doctor prescribed "9

<sup>8 This question about medication side effects is asked in an open-ended fashion rather than a specific fashion (e.g. "have you experienced nausea, vomiting or diarrhea after taking metformin") so as to not bias towards positive answers, given the high prevalence of gastrointestinal symptoms in Guatemalan patients, thought to be due in part to frequent exposure to and infection with gastrointestinal parasites  This question has been shown to predict outcomes in patients with chronic heart disease, as a proxy for

<sup>9 This question has been shown to predict outcomes in patients with chronic heart disease, as a proxy for medication adherence. It was also chosen for its simplicity. While self-reporting measures for adherence have been shown to correlate with objective adherence data, over-reporting of adherence is common. For this reason 47

#### [name]

- Answer choices (select one): All of the time (100%), Nearly all of the time (90%), Most of the time (75%), About half the time (50%), Less than half the time (<50%)

- Scoring
  - Those responding "All of the time" or "Nearly all of the time" are considered to be adherent
  - Those responding "Most of the time" or less are considered to be non-adherent
- "Did you take your full dosage of glibenclamide yesterday "10 (Y/N)
- If YES, application skips to the next question
  - If NO, application prompts promoter to ask patient "Did you take your full dosage of glibenclamide today "  $(Y/N) \rightarrow$  application moves on to the next section with either answer

# Appendix 4 - Hypoglycemia Protocol

# Protocol for identifying probable hypoglycemic episodes

- Patients who are taking glibenclamide are asked the following questions:
  - "In the last month, have you had episodes of any of the following symptoms":
    - Confusion
    - Trembling
    - Feeling uncoordinated
    - Palpitations
    - Abnormal sweating
    - Abnormal anxiousness
  - Patients reporting episodes of any of these symptoms are asked the following questions and their answers are scored as noted:
    - "Did these symptoms come on gradually or did they start suddenly"
      - Gradually (0)
      - Suddenly (+1)
    - "Did these symptoms occur when you had not eaten for several hours or after strenuous physical activity"
      - Yes (+1)
      - No (0)
    - "Did these symptoms improve after eating something
      - Yes (+1)
      - No (0)
- Patient considered to have probable hypoglycemia if above answers total to 2 or more points

and because the original validation study used this standard as well, we define adherence as taking medication "Nearly all of the time" or "All of the time".

<sup>10 Glibenclamide functions as an insulin secretagogue and has a duration of action of ~24 hours. Thus, it is expected to have a relatively short-term effect on blood glucose and it is essential to know the timing of the last dose when interpreting and acting on a patient's blood glucose level.

<sup>1These symptoms were found to be the most highly correlated with experimentally-induced hypoglycemia.

 <sup>12 In general, the onset of hypoglycemia symptoms is rapid rather than gradual
  This question assesses for the association of symptoms with two common risk factors for hypoglycemia that are likely to be present in our population

[name]

- Patients who have 2 or more points are asked the following question: "When you had these symptoms, were you so confused or sleepy that someone else needed to help you eat or drink something with sugar "
  - If YES, this is considered as an episode of probable severe hypoglycemia
  - If NO, this is considered an episode of probable mild hypoglycemia

